9.2 SURGERY VISIT

9.2.1 CLONIDINE-RANDOMIZED GROUP

On the day of surgery, just prior to the surgery, a blood draw will be done pre-intubation. The patient will be asked to fill out 1 questionnaire (STAI-C) and undergo MDT/PPT (Mechanical

Detection / Pain Pressure Threshold testing only). Another blood sample will be drawn post-intubation while the patient is still asleep.

At the end of the spinal surgery, both the CPM optimal and sub-optimal subjects who were randomized to the Clonidine group will receive intrathecal Clonidine 1 mcg/kg (up to 75 mcg).

The administration of the medication will only be done while patients are in well monitored setting. The intrathecal administration will be done post-operatively with optimal continuous hemodynamic monitoring. If required, atropine will be available in the operating room and the ward.

The anesthesia monitoring process and details of the surgical procedure will be collected for research purposes on the Anesthesia Data Collection and SDST Data Collections forms, respectively.

All Patients receiving the oral dose of clonidine or the placebo will undergo hemodynamic monitoring every 8 hours. Neuro-monitoring data as per standard of care (pain level assessments, level of drowsiness (Sedation Level Form), hemodynamic stability q2hr for the first 48hr, vital signs q1hr for 12h, then q2h for 12h, then q4hr for 24hr, then q8hr for 72hr) will be used for study purposes, as well, neuromonitoring surgical data will be collected on the SDIM (Spinal Deformity Intra-Operative Monitoring) worksheet and the Neurological Deficit Post-op form.

9.2.2 PLACEBO-RANDOMIZED GROUP

Both the optimal and sub-optimal groups who were randomized to the placebo group will receive intrathecal spinal morphine (5 mcg / kg) at the end of the spinal procedure in the operating room.

9.3 IN-HOSPITAL VISIT

Post-operatively, subjects will have their blood drawn on post-operative Day 1, 2 and 5. On Day 1 and 2 subjects will also undergo only the Mechanical Detection and Pressure Pain Threshold portion of the QST testing. On day 5, subjects will undergo the full QST testing. The subjects will be asked to fill out the following questionnaires on post operative day 1, 2 and 5 while they are in the hospital:

- ✓ Pain numerical rating scale for children (In-hospital – 7 questions)
- ✓ Tampa Scale for Kinesiophobia (TSK)
- ✓ Pain Catastrophizing Scale (PCS-C)

- ✓ PSQI (In-hospital)
- ✓ Adolescent Pediatric Pain Tool (APPT)
- ✓ Revised Children Anxiety and Depression Scale (RCADS) (Post Op Day 5 only)
- ✓ Patient's Global Impression of Change (PGIC)

These tests should take approximately 45 minutes.

9.3.1 CLONIDINE-RANDOMIZED GROUP

On Post-operative Day 1 through Day 5, both the CPM optimal and sub-optimal subjects who were randomized to the Clonidine group will be instructed to take 100 mcg pill three (3) times a day. Patients and treating team will be blinded to which pills they will be taking.

9.3.2 PLACEBO-RANDOMIZED GROUP

On Post-operative Day 1 through Day 5, both the CPM optimal and sub-optimal subjects who were randomized to the Placebo group will be instructed to take the placebo pill three (3) times a day. Patients and treating team will be blinded to which pills they will be taking.

9.4 DISCHARGE VISIT AND AT HOME PATIENT DIARY CALL - 1X/PER X 6 WEEKS

On the day of discharge, patients are assessed for any neurological deficits. These will be recorded on the SDIM Discharge form and included in the patient's study analysis.

Patients will be contacted by phone once a week for 6 weeks (or up until their 6 week visit). They will be asked about pain levels, medication intake, activity levels and their sleeping habits for the week in question. Their interview will be recorded on Patient Home Interview / Phone Call Form.

9.5 SIX (6) WEEKS AND SIX (6) MONTH FOLLOW-UP VISITS

At the 6-week and 6 month visits, the subject will be expected to complete the following:

- ✓ Pain intensity rating (self-reported)
- ✓ Approximately 10 mL of blood will be drawn and blood pressure will be taken
- ✓ Medical History Interview (Patient History - REVISIT Collection Form)

- ✓ Quantitative Sensory Testing (QST)

The patient will be asked to complete the following questionnaires:

- ✓ Pain numerical rating scale for children (6 questions)
- ✓ State-Trait Anxiety Inventory (STAI-C)
- ✓ Pain Catastrophizing Scale (PCS-C)
- ✓ Functional Disability Index (FDI)
- ✓ Revised Children Anxiety and Depression Scale (RCADS)
- ✓ Pittsburg Sleep Quality Index (PSQI)
- ✓ Neuropathic Pain Questionnaire (DN4)
- ✓ Tampa Scale for Kinesiophobia (TSK)
- ✓ Scoliosis Research Society (SRS-30)
- ✓ Adolescent Pediatric Pain Tool (APPT)
- ✓ Patient's Global Impression of Change (PGIC)

The visit should take approximately 1 hour

9.5.1 UNSCHEDULED VISITS

If subjects present for any unscheduled visits during the course of the study for any reasons, primary data sets will be collected in a prospective fashion. A separate data point will be added to ensure good documentation of any adverse event as the unscheduled visit may be related to the enrolment from the medications. Any additional pertinent outcome questionnaires or testing limited to the type of tests scheduled at the visit as described in section 9.5 are judged relevant by the PI or the coordinator. At minimum, the following data points will be collected:

- a) Cause of unscheduled visits
- b) Medications
- c) The subject will be expected to complete the following:
 - ✓ Pain intensity rating (self-reported)
- d) The patient will be asked to complete the following questionnaires:
 - ✓ Pain numerical rating scale for children (6 questions)

9.5.2 PREMATURE STUDY TERMINATION

Participation of the subject in the study may end for any of the following reasons:

- The subject/subject's representative withdraws informed consent for any reason
- Occurrence of an AE or SAE that prevents the subject from continuing in the study.
- Death
- The subject does not meet eligibility criteria / fails the screening process
- Physician discretion (e.g. Patient is non-compliant with protocol)
- The subject is lost to follow up
- The Sponsor/Investigator terminates the study

Documentation of reason(s) for subject's discontinuation in the study will be detailed and explained on a File Note and entered into the patient's study file.

10 STUDY AGENT INFORMATION

QST results will show that subjects either have an optimal or a sub-optimal response. The subjects who fall into the optimal category will be randomized to either Clonidine or placebo and the subjects who fall into the sub-optimal category will also be randomized into either Clonidine or placebo. The hospital pharmacy will do 1:1 randomization using online software.

Randomization and blinding of the medications and placebo will be performed by the hospital pharmacy. The pharmacy will be sent the list of patients participating in the study. They will maintain the trial treatment randomization codes, and procedures for breaking codes will be also carried out by the pharmacy.

For each study patient, the physician will supply the pharmacy with a prescription ordering medication for the Clonidine arm OR the placebo arm according to what the patient is randomized to. The pharmacy will prepare the appropriate medication kits, according to the randomization assignment, either containing vials of Clonidine or intrathecal morphine. For the day of surgery, the pharmacy will prepare a blinded kit containing the medication, preparation materials and instructions. Either the evening before, or the morning of the surgery, the research assistant will go to the pharmacy and pick up the blinded study medication kit and deliver it to the OR. The respiratory therapist will prepare the medication contained in the kit in the operation room just prior to surgery and then give it to the anesthesiologist who will administer it to the patient.

The 5 days of post-operative medication, either Clonidine or placebo, according to patient's randomization prescription, will be dispensed daily from the hospital's pharmacy, along with their regular routine medications.

As per Standard of care, concomitant therapy will be provided for pain, anti-nausea and for any other reasons that may occur. These therapies will be given in addition to the study medications.

All medications given to the patient will be noted in the patient's medical chart by the nurse. The patient's medical chart will then be verified daily by a research assistant for study drug compliance. In the event of non-compliance, a Note File will be added to the patient's study file listing the reasons why, and the action taken and filed in the patient's study file. Providing patients wish to remain in the study, they will not be discontinued from the study for non-compliant medication intake.

The hospital pharmacy will be responsible for the storage and stability of all medications and placebos and preparation of the blinded study kits. They will maintain the patient identification code list, randomization, drug accountability, and temperature logs.

Any unused medications will be returned to the hospital pharmacy for accountability purposes and for destruction as per hospital policy.

At the completion of the study, there will be a final reconciliation of drug shipped, drug consumed, and drug remaining. This reconciliation will be logged on the drug reconciliation form, signed and dated. Any discrepancies noted will be investigated, resolved, and documented prior to return or destruction of unused study drug. Any remaining drugs will be destroyed as per on site will be documented in the study files.

11 STUDY MEASURES

The following procedures are experimental and performed exclusively for research purposes.

11.1 SPECIMENS

11.1.1 BLOOD DRAW AND BLOOD PRESSURE READING

The nurse will blood draw approximately 10mL of venous blood and take the subject's blood pressure. The data will be recorded on the Blood Information Form.

10ml of blood will be drawn at various time points and will be processed for further analysis.

Although the role of inflammatory cytokines in pain sensitization is well-known, there relevance is yet to be fully understood (Clark, Old et al. 2013). Using antibody-based immunoassays, these inflammatory markers will be measured throughout the perioperative period.

More and more, the importance of epigenetic modifications in the development of chronic and/or neuropathic pain is being recognized (Denk and McMahon 2012, Sukenaga, Ikeda-Miyagawa et al. 2016, Chidambaran, Zhang et al. 2017). Global DNA methylation in blood will therefore be analyzed to see if any changes occurred following surgery and methylation state on the promoter of specific genes that have either been shown to be altered in chronic neuropathic states or that could be implicated in the pathology will be analyzed.

A genomic analysis of the sample will also be carried out. Chronic pain development after surgery results from complex biochemical and pathophysiological mechanisms that differ in type, although inter-related, among different surgical procedures [40]. Another explanation to understand why some patients do develop CPSP and others don't may reside in susceptibility factors that might be inherited and/or environment-related and can be assessed with a genomic approach [41]. According to the PainGene Database, about 300 genes are known to be relevant to pain and hundreds of pain-regulated genes have been identified by gene expression profiling studies [42]. Genetic variations may provide useful information to predict the intensity of postsurgical pain. Moreover, these variations may inform us on the sensitivity to anesthetics and analgesics regimen. Changes in the transcriptomes of patients undergoing major orthopedic surgery may also reflect anesthesia and analgesia-related expression profiles of various types of neurons, and information on such changes may contribute to personalized post-operative pain management. Furthermore, chemical modifications of DNA are epigenetic marks that constitute the functional genome and are key to generating diverse cellular phenotypes from the same genotype. These modifications and the cellular machineries that regulate them are essential for maintaining tissue-specific and timing-specific expression profiles for normal functioning [43] and can be altered in the post-operative context."

Ultimately, we hope to have a thorough understanding of the molecular alterations leading to pain while help developing more targeted line of treatments.

11.1.1.1 ALIQUOTING AND SPECIMEN RETENTION

The blood sample will be centrifuged, aliquoted and stored at -80°C pending biochemical analysis. The samples will be analyzed within 1 year. The samples are stored in a locked laboratory and only authorized research personnel are permitted to access this area. Sample accountability and storage location is tracked by research personnel on a spreadsheet maintained in a password-protected computer.

11.1.1.2 LABELING

All samples will be labeled with a study identification number and the time and date of collection. They will be stored in the laboratory's -80°C freezer pending analysis.

11.1.1.3 SPECIMEN ANALYSIS

Biochemical Assessment: Modulatory effects of the nociceptive transmission are largely mediated by descending monoaminergic pathways. A molecular assessment of monoamines involved in the dopaminergic and adrenergic pain pathways related to the endogenous pain inhibitory system (dopamine, serotonin, epinephrine, norepinephrine) will be performed. Analyses will be performed by liquid chromatography coupled with tandem mass spectrometry on TripleTOF 5600 mass spectrometer (AB Sciex Pte Ltd, Concord, Ontario, Canada) equipped with DuoSpray (AB Sciex) source. Data integration and analysis will be performed by selecting the appropriate ion

transition with a mass range of 0.05 0.05 0.05 MultiQuant software, version 2.0, with the signal finder algorithm (AB Sciex)

Genomic analysis: DNA will be extracted from the buffy coat containing the white blood cells of collected blood samples through the QIAGEN DNA Mini Kit. The DNA will then be further analyzed for specific single-nucleotide polymorphisms (SNPs) (rs4633, rs4680, rs4618 and rs165774) via TaqMan Genotyping Assay. This process involves amplification of specific DNA fragments by PCR followed by analysis on an optical plate for specific genetic polymorphisms, to identify which patients carry such polymorphisms.

11.1.1.4 DESTRUCTION OF SPECIMENS AT STUDY COMPLETION

All specimens, at the end of the study, will be destroyed as per the hospital's biohazard waste management policy.

11.2 QUANTATITIVE SENSORY TESTING (QST)

11.2.1 MECHANICAL DETECTION THRESHOLD (MDT)

The Research Assistant will use TouchTest Sensory Evaluators (filaments) with varying diameters (forces ranging between 0.008-300 grams) and apply stimulation on the forearm, which will serve as the control site, as well as on the painful segment (affected area – where back pain is located).

11.2.1.1 DATA COLLECTION AND TOUCH TEST SENSORY EVALUATOR PREPARATION

The Research Assistant will start by entering the required information on the MDT Data Collection Form, as well as setting up the 5 TouchTest Sensory Evaluators (filaments) that will be used during testing (1g, 0.6g, 0.4g, 0.16g, 0.07g). The Research Assistant will demonstrate the procedure using the subject's palm of their hand.

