11.2.1.2 CONTROL TEST SITE

The subject will rest their arm on a comfortable surface and be instructed to keep their eyes closed throughout the duration of the test. On the subject's left forearm, one inch from the crook of their elbow, with a washable marker, a 1 inch by 1 inch square box is to be drawn and a dot placed in the middle of the box. Using the filaments, and starting with the smallest filament, stimulation will be applied from a 90 degree angle to the dot, not exceeding 1 second of stimulation. With each application of stimulation, inform the subject you will be touching them by saying "now". The subject should respond yes or no to feeling the touch. The results are to be recorded on MDT Data Collection Form.

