11.2.1.4 MDT DETAILED TEST PROCEDURE

Procedure - Descending

This test procedure should be followed for both the control and pain test site.

1. Begin at filament (1g) (higher if the subject does not feel this force) on marked location.
2. If the subject feels the filament, present the next thinner filament, (0.6g). Continue to present thinner and thinner filaments until the subject no longer detects the touch.
3. Record the LAST DETECTED FORCE in grams (the filament above the one the subject did not feel).

Procedure - Ascending

4. Begin with the filament that was noted as last detected force, and begin moving up to next thicker filaments, augmenting the force each time.
5. Continue until the subject feels the touch again.
6. Note the FIRST DETECTED force in grams.
7. Repeat the descending and ascending procedures for a total 3 times of each.

NOTE: If the subject does not feel the initial (1g) filament, move up 3 filaments (e.g. 4g). Keep repeating this until the patient feels the touch. Then proceed with the protocol using the newly selected filament.

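### The protocol disagrees with itself on which filaments the mechanical detection threshold uses, and has no rule for a patient who feels 0.07 g

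*Combined protocol and SAP*

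**What the plan says.** Four parts of section 11.2.1 bear on this.

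- Section 11.2.1 describes filaments "with varying diameters (forces ranging between 0.008-300 grams").
- Section 11.2.1.1 has the assistant "setting up the 5 TouchTest Sensory Evaluators (filaments) that will be used during testing (1g, 0.6g, 0.4g, 0.16g, 0.07g").
- Section 11.2.1.4, descending series: "Continue to present thinner and thinner filaments until the subject no longer detects the touch". The value kept is then defined: "Record the LAST DETECTED FORCE in grams (the filament above the one the subject did not feel"). The ascending series starts from that force and moves only to thicker filaments.
- The note in section 11.2.1.4 covers the insensitive end: "If the subject does not feel the initial (1g) filament, move up 3 filaments (e.g. 4g"). No matching note covers the sensitive end.

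The starting point also differs. Section 11.2.1.2 has "starting with the smallest filament, stimulation will be applied from a 90 degree angle to the dot", and section 11.2.1.3 says the same for the pain site. Section 11.2.1.4, which is meant for both sites, says: "Begin at filament (1g) (higher if the subject does not feel this force) on marked location".

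**The concern.** The descending rule needs one filament that is not felt. Within the five listed, a patient who feels 0.07 g never fails one, so the rule does not end and the recorded force is undefined. The ascending series cannot rescue the reading, because it starts at the last detected force and goes up.

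Two things can then happen. An assessor who keeps to the list will probably write 0.07 g, and a censored value enters the data as if it were measured. An assessor who reads section 11.2.1 and the open-ended descending step will reach for a thinner filament and record a lower value. The same patient could get different values from different assessors, or at different visits, with no change in her threshold.

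MDT is repeated often. The study plan table marks it at baseline, surgery, days 1, 2 and 5, six weeks and six months. On the day of surgery and on days 1 and 2 it is one of only two sensory tests done (sections 9.2.1 and 9.3). Section 9.1 counts it within the sensory testing that the primary objective in section 6 wants to use as a predictor, and section 16.4 plans a secondary analysis of change in sensory testing over time. Unrecognised censoring would tend to weaken an association with MDT and shrink any downward shift.

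**Working it through.** The plan states no MDT figure, so there is nothing to reproduce. The check sets the sections side by side and then illustrates the possible size.

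**1. Endpoint for a patient who feels 0.07 g**

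| Filaments taken as available | Thinner filament to present? | Descending endpoint |
|---|---|---|
| Five in 11.2.1.1 (1, 0.6, 0.4, 0.16, 0.07 g) | No | None; at best recorded as 0.07 g |
| Range in 11.2.1 (0.008 to 300 g) | Yes | Defined, unless 0.008 g is also felt |

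Under neither reading is there a code for a patient who feels the thinnest filament.

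**2. Range at stake.** From 0.07 g down to 0.008 g is log10(0.07/0.008) = log10(8.75) = 0.94 log10 units. The five filaments span log10(1/0.07) = 1.15. The unlisted lower stretch is therefore nearly as wide as the listed one.

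**3. Share of readings at the floor.** This rests on an assumption: true thresholds are log-normal with median M and standard deviation s on the log10 scale. A patient feels 0.07 g when her threshold is at or below it, so

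share = Φ[(log10 0.07 − log10 M) / s].

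Example with M = 0.16 g and s = 0.3: (−1.155 + 0.796)/0.3 = −1.20, giving 11.6%.

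| Assumed median | s = 0.2 | s = 0.3 | s = 0.4 | s = 0.5 |
|---|---|---|---|---|
| 0.4 g | 0.0% | 0.6% | 2.9% | 6.5% |
| 0.16 g | 3.6% | 11.6% | 18.5% | 23.6% |
| 0.07 g | 50% | 50% | 50% | 50% |

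With 0.008 g in place of 0.07 g in the formula, the largest share in the same twelve cases is 3.0% (M = 0.07 g, s = 0.5).

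These are shares of readings without a valid endpoint under the list of five. The share whose recorded value would change is smaller: a patient who feels 0.07 g but not the next thinner filament would correctly be recorded at 0.07 g. The documents do not list the filaments between 0.07 and 0.008 g, so that smaller share is not computed.

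**The case against.** The strongest reply is that no floor is stated. Section 11.2.1 names forces down to 0.008 g, the descending step has no lower limit, and the 4 g example lies outside the five, so the list is not closed. A sensible assessor would take the next thinner filament. The MDT Data Collection Form is not in the documents and may carry its own rule. This stands in part: flooring depends on following 11.2.1.1 literally, so one cannot say that sensitive patients are floored. It does not remove the disagreement between sections, and an unwritten choice left to the assessor is itself a source of variation.

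A reader might also infer that the floor hides sensitised patients. The documents do not support that. MDT here is a yes/no answer to feeling a touch. Section 2.1 links central sensitisation to temporal summation, and pain sensitivity is tested separately by pressure, heat and conditioned pain modulation (CPM). What can be said is that low detection thresholds, and falls in them, may be censored.

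The percentages are fairly challenged too. They follow wholly from the assumed distribution and treat thresholds as continuous, whereas the procedure uses discrete filaments in three descending and three ascending series. They show that the floor could be trivial or large, and no more.

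Finally, MDT carries little of the trial's main inference. The primary endpoint is the 0–10 pain rating, patients are grouped by CPM, and there is no MDT cut-off or MDT hypothesis. That stands and sets the weight of the point.

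**Conclusion.** Sections 11.2.1, 11.2.1.1 and 11.2.1.4 do not agree on the filaments used, and no rule covers a patient who feels 0.07 g. If the list of five is followed, her MDT is left-censored at 0.07 g. If practice varies, values are not comparable across patients or visits. The size cannot be derived from the documents. Under the log-normal assumption it runs from negligible at a median of 0.4 g to half of readings at 0.07 g, and a median below 0.07 g would put more than half there. The effect is confined to MDT as a sensory predictor and to the secondary analysis of sensory testing over time. The primary endpoint, the CPM strata and the sample size are unaffected. This is a minor point, worth settling because a threshold not measured at the visit cannot be recovered later.

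**What to change.** 1. In 11.2.1.1, set out the filaments below 0.07 g as well, down to the 0.008 g named in 11.2.1.
2. In 11.2.1.4, add the counterpart of the upward note: if 0.07 g is felt, the series continues down to the thinnest filament. A patient who still feels that one is coded as at or below its force.
3. In 16.4, state that values so coded are treated as left-censored and not as measured forces.
4. Reconcile the starting filament: the smallest in 11.2.1.2 and 11.2.1.3 against 1 g in 11.2.1.4. This affects every patient at every MDT session.

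The cost is wording plus some testing time for sensitive patients. Each added filament that has to be presented means up to 3 descending series × 2 sites = 6 more applications per session, plus the occasional false presentation. Other patients are unaffected, and no sample size, power or alpha changes.
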